### **8.1. Statistical Analysis Methods**

#### **8.1.1. Plasma Concentration**

Individual subject concentration data will be listed and summarized using descriptive statistics. Summary statistics (n, mean, StD, coefficient of variation [%CV], median, min, max, Q1, and Q3) will be presented by time point. Moreover, the geometric mean, 95% CI of the natural log-transformed values will be presented.

Individual concentration data listings and summaries will include all subjects in PK Analysis Set. The sample size for each time point will be based on the number of subjects with nonmissing concentration data at that time point. The number of subjects with concentration BLQ will be presented for each time point. For summary statistics, BLQ values will be treated as 0 at predose and one-half of the lower LOQ for postdose time points.

The listing of PK plasma concentrations sampling details by subject including deviations in scheduled and actual draw time and procedures will be provided.

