8.3.2. Pharmacokinetic/Pharmacodynamic Analysis Sets

The Pharmacokinetic/Pharmacodynamic analysis sets include subjects in the full analysis set who have the necessary baseline and on-study measurements to provide interpretable results for specific parameters of interest. These analysis sets will be used in the analyses of GS-9973 drug levels and changes in CD63 expression in peripheral blood basophils. Analysis for GS-9973 SDD and original formulation will be done separately.

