- q Subjects with LPL/WM only. This procedure should be conducted on the Day 1 visit occurring during the week window allotted for tumor response assessments.
- r Includes date/time of last dose of GS-9973 (excluding Day 1 of Cycle 1)
- s Collect on Cycle 2, Day 15 only
- t On Day 1 of Cycle 1, samples will be collected pre-dose, 1.5 hours post-dose (± 10 minutes) and 4 hours post-dose (± 10 minutes); on cycle 1 day 8 (predose and 4 hours post dose) and cycle 1 day 15 (predose)
- u For CLL dose ranging, CLL prior BTK inhibitor exposure, or CLL prior PI3K inhibitor exposure cohorts only
- v Excluding subjects off study drug at time of progression
- w Samples will be collected pre-dose on Cycle 1 Day 1, Cycle 12 Day 1 and at Disease Progression or EOS only
- x May be collected up to 2 days prior to the Day 1 visit

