##### **3.1.4. Pharmacokinetic Analysis Sets**

The Pharmacokinetic (PK) Analysis Set will include all enrolled subjects who took at least one dose of study drug (ie, ENTO) and have at least one nonmissing postdose concentration value reported by the PK laboratory. This is the primary analysis set for all PK analyses.

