Concentration values that are below the limit of quantitation (BLQ) will be presented as “BLQ” in the concentration data listing. Values that are BLQ will be treated as 0 at predose time points, and one half the value of the LOQ at postdose time points for summary purposes. Concentration values that are BLQ will be imputed as one-half LOQ before log transformation.

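### SAP 8.1.1 pools predose samples drawn during a temporary dose interruption with on-treatment troughs, which lowers the on-drug exposure summaries, the geometric mean most of all

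*SAP*

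**What the plan says.** SAP 8.1.1 governs the concentration tables. On who is included: "Individual concentration data listings and summaries will include all subjects in PK Analysis Set". On which values are included: "The sample size for each time point will be based on the number of subjects with nonmissing concentration data at that time point". Membership of the PK Analysis Set is decided per subject; besides one dose, SAP 3.1.4 asks only that the subject "have at least one nonmissing postdose concentration value reported by the PK laboratory".

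Two general sections reinforce this. SAP 3.6.2 keeps all data and plans no outlier sensitivity analysis. SAP 3.8.2 uses the nominal visit and derives no analysis window. SAP 3.2 sets the default columns: cohort, prior treatment status or dose level.

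For BLQ values SAP 8.1.1 states: "For summary statistics, BLQ values will be treated as 0 at predose and one-half of the lower LOQ for postdose time points". For the log scale, SAP 3.7 states: "Concentration values that are BLQ will be imputed as one-half LOQ before log transformation".

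On the collection side, Protocol 6.3.1 and 6.3.2 have sites record the approximate hours from the last two doses to the PK draw, and SAP 4.2.2 lists dose interruptions. The one instruction about off-drug samples is Protocol Appendix 2, footnote v: "Excluding subjects off study drug at time of progression". Nothing comparable covers a temporary interruption.

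**The concern.** PK draws follow the cycle calendar (Protocol 6.3.1, 6.3.2 and Appendix 2, footnote p), while Table 5-4 withholds dosing for several toxicities until they improve. A scheduled predose draw can therefore fall inside an interruption. Followed literally, the SAP enters that value as a trough in the subject's cohort or dose column, although it does not describe exposure on that dose.

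Exposure is a secondary objective (Protocol 2.1, SAP 1.1). The dose ranging cohort has about 20 subjects per dose level, so a single off-drug value is 5% of the data at a time point. If interruptions are more frequent at one dose than another, the distortion differs between the columns a reader will compare.

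**Working it through.** The plan states no numerical result for the PK summaries, so there is no figure to reproduce. The one related rate checks: 11/109 = 10.1%.

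**Inputs from the documents**
- Half-life about 10 h, with levels minimal at 48 h (Protocol 5.5.9).
- Grade 3 or 4 transaminase elevations that declined on holding drug: 11 of 109 subjects (Protocol 1.7.1).
- Reported times to Grade 1 or less after interruption: 7, 12, 21 and 27 days (Protocol 1.6.2); mean (7 + 12 + 21 + 27)/4 = 16.75 days.
- About 20 subjects per dose level (Protocol 3.1.2).

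**Assumptions, because the documents give no figure**
- LOQ of 1 to 10 ng/mL.
- Typical on-drug trough T of 275 to 923 ng/mL. This borrows the two EC70 values in Protocol 1.5.5 purely as a scale.
- Between-subject CV of 60%, used only for the simulation.

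**Step 1: what an off-drug sample reads.** The fraction left h hours after the last dose is 2^(−h/10). At 48 h it is 3.6%, which agrees with the protocol's description. Relative to a 12 h trough the fraction is 2^(−(h−12)/10): 8.2% at 48 h and 0.002% at 7 days. The level reaches the LOQ at h = 12 + 10·log2(T/LOQ), which is 60 h for T = 275, LOQ = 10 and 110 h for T = 923, LOQ = 1. Samples later than that in an interruption are BLQ.

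**Step 2: plausible share of samples off drug.** From transaminase interruptions alone, assuming all 11 subjects were held for the mean 16.75 days, f = (11/109) × 16.75/W. This is 1.0% if the interruptions are spread over W = 168 days, 3.0% over 56 days and 6.0% over 28 days.

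**Step 3: effect on the means.** With a share f off drug and BLQ:
- Geometric mean change = ((LOQ/2)/T)^f − 1. Example: (5/275)^0.05 − 1 = −18.2%.
- Arithmetic mean change = −f when BLQ is set to 0.

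| f | GM: T 275, LOQ 10 | GM: T 275, LOQ 1 | GM: T 923, LOQ 10 | GM: T 923, LOQ 1 | Arithmetic mean |
|---|---|---|---|---|---|
| 1% | −3.9% | −6.1% | −5.1% | −7.2% | −1.0% |
| 3% | −11.3% | −17.2% | −14.5% | −20.2% | −3.0% |
| 5% | −18.2% | −27.1% | −23.0% | −31.3% | −5.0% |
| 6% | −21.4% | −31.5% | −26.9% | −36.3% | −6.0% |

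An off-drug sample drawn early, before the level is BLQ, pulls less. At 48 h and f = 5% the factor is 0.0825^0.05 = 0.883, a fall of 11.7%.

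**Step 4: 1 of 20 subjects off drug, simulated** (lognormal, 20,000 runs). The median falls 3.5%. The %CV is about 63% with the off-drug value kept and about 57% without it. The 95% CI half-width of the log geometric mean is 0.49 to 0.83 with it and 0.26 without it.

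**Step 5: the BLQ convention.** Using LOQ/2 instead of 0 at predose changes the arithmetic mean by f × (LOQ/2)/T. The largest case, f = 10.1% with T = 275 and LOQ = 10, is 0.101 × 5/275 = 0.2 percentage points. The geometric mean does not change, because SAP 3.7 already uses LOQ/2 there.

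**The case against.** **Exposure as received.** The objective is to evaluate exposures in these subjects. If that means exposure as actually experienced, interruptions included, the all-samples summary is fair and excluding values moves it upward. This stands in part. The SAP does not say which is meant, so downward bias can be claimed only for on-drug exposure, and the all-samples summary deserves to be kept.

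**Existing safeguards.** SAP 8.1.1 gives the BLQ count per time point, the median and quartiles, individual concentrations and a listing of draw-time deviations; SAP 4.2.2 lists interruptions. An off-drug BLQ trough could be traced. That helps a careful reader but leaves the summary unchanged.

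**Limited stakes.** The tables are descriptive, follow study completion and go into a synoptic report. No passage makes them the basis for comparing doses with the EC70 values, and Protocol 3.2 ties regimen selection to emerging data. The 11/109 rate comes from 800 mg BID of the MM formulation and may not carry over to SDD doses. All of this stands and limits the weight of the point.

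Four stronger readings are tempting but not supported:
- *Setting predose BLQ to 0 adds materially to the error.* The convention ("Values that are BLQ will be treated as 0 at predose time points") fits the sample before the first dose, and elsewhere Step 5 shows it is almost inert.
- *The SAP dropped a sample-level filter from Protocol 8.3.2.* That section is itself subject-level: it admits subjects "who have the necessary baseline and on-study measurements to provide interpretable results for specific parameters of interest" and excludes no individual samples.
- *Footnote v shows the protocol bars off-drug samples generally.* It concerns the progression sample only. Its text is carried into SAP Appendix 1, although the lettering has shifted: the plasma concentration row still cites v, while the text now stands under w.
- *Draw-time scatter adds to the downward bias.* The ±4 h tolerance is stated only for Cycle 2 Day 1 (Protocol 6.3.1). Draws at 8 h and 16 h differ 2^(8/10) = 1.74-fold, yet both lie inside that window, and such scatter runs both ways.

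**Conclusion.** The point holds for temporary interruptions. The SAP states a complete inclusion rule that pools off-drug predose values with on-treatment troughs, so this is more than a missing detail, and for on-drug exposure the direction is downward. The cause is keeping the off-drug sample, not the value assigned to BLQ.

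The size is conditional on the assumed LOQ and trough ranges and on the off-drug samples being BLQ: a geometric mean lower by about 4–7% at a 1% share, 11–20% at 3% and 18–31% at 5%. No single figure should be quoted as the expected bias. The arithmetic mean and median move much less, and the precision of the geometric mean suffers as well.

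The point does not extend to dose changes. Reductions lower levels in a column, while escalation of lower-dose subjects (Protocol Synopsis) raises them, so the net direction there is not settled. Nor does the SAP say whether PK columns use planned or actual dose. The change is worth making before the analysis, but the trial's main conclusions do not rest on it.

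**What to change.** Amend SAP 8.1.1 along these lines:

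- Using the recorded hours from the last two doses and the interruption records, flag every sample after Cycle 1 Day 1 that was drawn during a dose interruption.
- Keep flagged samples in the listing, with the flag shown, and exclude them from the main time-point summary.
- Report the number excluded at each time point, by cohort or dose column.
- Repeat the summary with all samples as a sensitivity analysis, labelled as exposure as received.
- Apply the 12 ± 4 h criterion only at Cycle 2 Day 1. A window at any other visit would be new and would have to be declared as such.

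Optionally, limit the zero value for BLQ in SAP 3.7 to the sample before the first dose. This is tidier, with negligible numerical effect.

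The cost is a few sentences in the SAP, a small programming step on data already collected, one repeated table, and a few fewer samples at some time points. No further data collection is needed.

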## 9. PHARMACODYNAMIC (PD) ANALSES

In the synoptic CSR, the following exploratory endpoints of PD will not be provided:

- CCI [REDACTED]
- [REDACTED]

## **11. SOFTWARE**

SAS® Software Version 9.4 or higher, SAS Institute Inc., Cary, NC, USA.

## 12. SAP REVISION

Revision Date (dd month, yyyy)	Section	Summary of Revision	Reason for Revision

### 13. APPENDICES

#### Appendix 1. Schedule of Assessments

Study Phase	Screening	Cycle 1 (28 days)	Subsequent Cycles (28 days)	Safety Monitoring Visits	Tumor Response Assessments	Disease Progression or EOS c	30-Day Follow Up
Cycle Day	Screening	1	1	Varies a	Q8 or 12 wks or 6 months b	N/A	
Window	-35		±2 days	±2 days		N/A	
Study Assessments							
Informed Consent	X						
Medical History	X						
Physical Exam d	X	X	X	X		X	
Vital Signs e	X	X	X	X		X	
12-lead ECG	X			X			
Karnofsky Performance Status	X	X	X	X		X	
Prior/Concomitant Meds	X	X	X	X		X	
AEs f	X	X	X	X		X	X
CT or MRI	X g				X h	X i	
Bone Marrow Biopsy and Aspirate					X j	X j	
DLBCL Subtyping k		X					
Collect Archival Tumor Tissue (if available)		X l					
Complete Subject/Visit info in IxRS	X	X	X			X	

Study Phase	Screening	Cycle 1 (28 days)	Subsequent Cycles (28 days)	Safety Monitoring Visits	Tumor Response Assessments	Disease Progression or EOS c	30-Day Follow Up
Cycle Day	Screening	1	1	Varies a	Q8 or 12 wks or 6 months b	N/A	
Window	-35		±2 days	±2 days		N/A	
Sample Collection							
Chemistry	X	X	X x	X		X	
Beta-2-microglobulin		X	X			X	
Hematology	X	X	X x	X		X	
Coagulation	X	X	X x	X		X	
Urinalysis	X	X	X				
HBV, HCV and HIV Virology	X						
Pregnancy Test n	X	X	X	X		X	
GS-9973 Plasma Concentration o, p, v		X	X	X		X	
Buccal Swab u		X					
CCI							
Serum monoclonal IgM SPEP/IFE and cryoglobulin testing q		X			X		
Study Drug Dosing							
GS-9973 up to 800 mg BID Fasting or 100, 200 or 400 mg GS-9973 SDD BID Fasting			X			X	
Dispense Study Drug		X	X				
Study Drug Compliance f		X	X			X	
Collect Used/Unused Study Drug w			X			X	
For CLL, SLL and MCL subjects only							

Study Phase	Screening	Cycle 1 (28 days)	Subsequent Cycles (28 days)	Safety Monitoring Visits	Tumor Response Assessments	Disease Progression or EOS c	30-Day Follow Up
Cycle Day	Screening	1	1	Variesa	Q8 or 12 wks or 6 monthsb	N/A	
Window	-35		±2 days	±2 days		N/A	
Cytokines and Chemokines		X m	X m	X m		X	
CTC Molecular Characterization		X		X s		X	
CTC RNA w		X w	X w			X w	
CLL ONLY: Pharmacodynamic Measurements (BAT Assay)		X t					
CLL ONLY: Pharmacogenomic Testing		X		X s		X	

a Days 8, 15, and 22 of Cycle 1 and Day 15 of Cycle 2

b Tumor assessments will be performed every 8 weeks during the first 24 weeks of the study and then every 12 weeks thereafter regardless of cycle number and regardless of dose interruptions. Tumor assessments may be performed at other timepoints during the treatment phase as clinically indicated (to assess tumor progression). After week 72 scans will occur at least every 6 months (± 4 weeks). The same evaluation procedures must be used throughout the study for each subject. Scans should be of high quality and digitalized in the DICOM format to allow for reading at a centralized facility.

c If a subject stops study drug for a reason other than progressive disease and consistent with good medical practice, they will be followed as per the scheduled imaging in Section 6.5 with additional CBC (hematology) at time of assessments.

d Complete physical examination will be performed at Screening and at Disease Progression or EOS. A modified physical examination capturing changes from prior exams will be performed at other visits. Weight should be measured (in kilograms) at each physical examination. Height will be measured (in centimeters) at Screening only.

e Vital signs (including blood pressure, respiratory rate, pulse, oxygen saturation by pulse oximetry and temperature) should be taken after the subject has been sitting for at least 5 minutes.

f Adverse events will be assessed once ICF is signed, pre and post dose during applicable clinic visits, and 30 (±7) days following completion of the subject's last dose of study drug. Subjects should be contacted by phone (or in person, if necessary) 30 days (± 7 days) after the subject's last dose of study drug to assess AEs. Subjects should specifically be asked about the development of any adverse events since stopping the study.

g CT or MRI scans of neck, chest, abdomen, and pelvis taken as part of standard medical practice up to 35 days prior to Day 1 of Cycle 1 visit are acceptable for use at the Screening. Subjects with LPL/WM who previously failed screening for this study, due to an absence of lymphadenopathy on CT or MRI scans, do not need to be re scanned if the scans were performed within 16 weeks of first study drug administration to meet eligibility criteria.

h At all timepoints after Screening imaging of the chest, abdomen, and pelvis will be required. Imaging of the neck is required at each follow up time point if the neck scan was positive at baseline or if palpable neck lymphadenopathy appears during the course of the study.

i Tumor evaluations should be conducted at the End of Study Visit if not conducted in the previous 4 weeks. If a subject permanently discontinues study drug prior to objective documentation of progression, investigators should continue further follow up at the ~8 or ~12 week intervals until progression is documented.

j A bone marrow biopsy and aspirate will be collected for all subjects who achieve a CR for confirmatory purpose. For CLL subjects a bone marrow biopsy/aspirate will be collected to confirm a PD. If the subject does not otherwise meet criteria for CR or if the nature of PD does not require bone marrow confirmations, it is not necessary to obtain a bone marrow biopsy/aspirate (See Sections 6.18 and 6.20).

- k If the subject has DLBCL, subtyping is required. Submission of 15 unstained slides is required for subtyping if the subtype is not already known. Subjects for whom tissue is not available but the subtype is already known may be included if approved by the Medical Monitor following discussion with the investigator.
- l Fifteen recently prepared unstained slides from archival tumor tissues will be collected. Efforts to acquire tissue sample should begin on Day 1 of Cycle 1.
- m Collect on Cycle 1 Day 1, Cycle 1 Day 8, Cycle 2 Day 1 and Cycle 12, Day 1 only
- n For females of childbearing potential, a serum pregnancy test will be performed at Screening and urine pregnancy tests will be performed on Days 1 of each Cycle and Day 15 of Cycles 1 & 2 and at EOS.
- o Record the approximate number of hours between the last 2 doses of GS 9973 and the time the blood samples for plasma concentration were obtained
- p GS 9973: PK samples will be collected on Day 1 of Cycle 1 pre dose, 1.5 hours post dose and 4 hours post dose; on Day 1 of Cycles 2-6 pre dose (12 hours post last dose).
- q GS 9973 SDD: PK samples will be collected on Day 1 of Cycle 1 pre dose, 1.5 hours post dose and 4 hours post dose; on Day 8 of Cycle 1 pre dose, 1.5 hours post dose and 4 hours post dose; on Days 15 and 22 of Cycle 1 pre dose and 1.5 hours post dose; and on Day 1 of subsequent cycles pre dose and 1.5 hours post dose.
- r Subjects with LPL/WM only. This procedure should be conducted on the Day 1 visit occurring during the week window allotted for tumor response assessments.
- s Includes date/time of last dose of GS 9973 (excluding Day 1 of Cycle 1)
- t Collect on Cycle 2, Day 15 only
- u On Day 1 of Cycle 1, samples will be collected pre dose, 1.5 hours post dose ( $\pm$  10 minutes) and 4 hours post dose ( $\pm$  10 minutes); on cycle 1 day 8 (predose and 4 hours post dose) and cycle 1 day 15 (predose)
- v For CLL dose ranging, CLL prior BTK inhibitor exposure, or CLL prior PI3K inhibitor exposure cohorts only
- w Excluding subjects off study drug at time of progression
- x Samples will be collected pre dose on Cycle 1 Day 1, Cycle 12 Day 1 and at Disease Progression or EOS only
- y May be collected up to 2 days prior to the Day 1 visit

## Appendix 2. PFS Definition and Derivation Diagram

Progression-free survival (PFS) is defined as the interval from the first dosing date of study drug to the earlier of the first documentation of definitive disease progression or death from any cause.

Definitive disease progression for NHL is defined in the Protocol Section 6.20 based on standardized criteria {Cheson 2007, Rourke 2010} as specifically modified for this study to reflect the biology of the diseases under study and the pharmacology of study drug and the methods to be used in evaluation. The determination of CLL response and progression is defined in the Protocol Section 6.21 based on standardized IWCLL criteria {Hallek 2008} as specifically modified for this study considering the pharmacology of ENTO and the methods to be used in evaluation. The progression should be identified by relevant radiographic imaging assessments and pertinent clinical data by IRC and investigators. For this study, the IRC assessments will be used as primary PFS analyses. The date of definitive progression will be the time point at which progression is first identified. The death from any cause to be considered as PFS event should occur within the time window of 2 consecutive scheduled post-baseline tumor assessments after the last tumor assessment.

Subjects without progression or death will be censored at the last adequate post-baseline tumor assessment time. The adequate tumor assessments for determining censoring dates include complete response (CR), partial response (PR), minor response (MR), stable disease (SD), progressive disease (PD), and very good partial response (VGPR) or minor response (MR) for subjects with LPL/WM. Non-evaluable (NE), not assessed, and not applicable are considered as not adequate.

Subjects will be censored on the date of Study Day 1 if

- no adequate baseline tumor assessment is available and subject didn't die before or on the 2nd scheduled post-baseline tumor assessment without receiving anti-cancer therapy;
- or if no adequate post-baseline tumor assessment is available and subjects didn't die
- or if no adequate post-baseline tumor assessment is available and subjects died after the 2nd scheduled tumor assessment.

Subjects will be censored on the date of last adequate post-baseline tumor assessment, or Study Day 1 if the last adequate post-baseline tumor assessment doesn't exist, for the following situations:

- who do not have documented progression or die, or
- who start new anti-cancer therapy before documented progression, or
- who start new anti-cancer therapy before death without documented progression, or
- who have  $\geq 2$  consecutive missing post-baseline tumor assessments immediately before documented progression, or

- who have  $\geq 2$  consecutive missing post-baseline tumor assessments immediately before death without documented progression

Table 13-1 below lists detailed event/censoring scheme for PFS derivation and the derivation diagram lists all decisions on event/censoring indicators and time.

